2 ELIGIBILITY ASSESSMENT AND ENROLLMENT

2.1 ELIGIBILITY CRITERIA

2.1.1 Inclusion Criteria

- Histologically proven ACC with the majority of disease confined to the peritoneal cavity and resectable or amenable to radiofrequency ablation
- Disease evaluable by CT or PET imaging
- All disease should be deemed resectable based on imaging studies e.g.:
 - Hepatic metastases (unilateral or bilateral ≤ 5 lesions, ≤ 15 cm total diameter)
 - **Note:** Hepatic lesions must be amenable to complete resection
 - Primary peritoneal metastases (small disease load $\leq P2$ disease) without massive ascites or intestinal obstruction
 - Lung metastases (≤ 3 unilateral/bilateral, 9 cm total diameter)
 - **Note:** lung lesions must be amenable to complete resection
 - **Note:** Patients with both pulmonary and hepatic metastases will be enrolled at the discretion of the PI
 - **Note:** In situations where resection to Completeness of Cytoreduction Score (CC) 0 or 1 is uncertain, patients may undergo diagnostic laparoscopy prior to enrollment to determine feasibility of resection. (**Appendix D**)
- Greater than or equal to 18 years of age
- Able to understand and sign the Informed Consent Document

- Clinical performance status of ECOG ≤ 2
- Life expectancy of greater than three months
- Patients of both genders must be willing to practice birth control during and for four months after receiving chemotherapy
- Hematology:
 - Absolute neutrophil count greater than 1500/mm³ without the support of Filgrastim.
 - Platelet count greater than 75,000/mm³.
 - Hemoglobin greater than 8.0 g/dl.
- Chemistry:
 - Serum creatinine less than or equal to 1.5 mg/dl unless the measured creatinine clearance is greater than 60 mL/min/1.73 m²
 - serum AST and ALT within 5 times the upper limit of normal and a total serum bilirubin of less than 3 times the upper limit of normal, both of which define the upper limit of grade 2 treatment related toxicities.
 - PT within 2 seconds of the upper limit of normal (INR \leq 1.8)
- Recovered from any toxicity to grade 2 or less from all prior chemotherapy, immunotherapy or radiotherapy and be at least 30 days past the date of their last treatment with the exception of mitotane which may be continued.
- Able to understand their disease and the exploratory nature of combining surgery and HIPEC for this histology.

2.1.2 Exclusion Criteria

- Concomitant medical problems that would place the patient at unacceptable risk for a major surgical procedure.
- History of congestive heart failure and/or an LVEF < 40%
- **Note:** Patients at increased risk for coronary artery disease or cardiac dysfunction (e.g., >65yo, diabetes, history of hypertension, elevated LDL, first degree relative with coronary artery disease) will undergo full cardiac evaluation and will not be eligible if they demonstrate significant irreversible ischemia on stress thallium or an ejection fraction <40%.
- Significant COPD or other chronic pulmonary restrictive disease with PFT's indicating an FEV1 less than 50% or a DLCO less than 40% predicted for age
Note: Patients who have shortness of breath with minimal exertion or who are at risk for pulmonary disease (e.g., chronic smokers) will undergo pulmonary function testing and will not be eligible if their FEV1 is < 50% of expected.
- Grade 2 or greater neuropathy
- Women of child-bearing potential who are pregnant or breastfeeding because of the potentially dangerous effects of the chemotherapy on the fetus or infant.
- Brain metastases or a history of brain metastases
- Childs B or C cirrhosis
- Evidence of severe portal hypertension by history, endoscopy, or radiologic studies
Note: Any diagnosis of portal hypertension or clinical stigmata of such including but not limited to gastric or esophageal varices, umbilical vein varices or telangectasias.
- Weight < 30 kg

- Active systemic infections, coagulation disorders or other major medical illnesses of the cardiovascular, respiratory or immune system, myocardial infarction, cardiac arrhythmias, obstructive or restrictive pulmonary disease

2.2 SCREENING EVALUATION

2.2.1 Within 6 weeks prior to treatment:

- HIV, Hepatitis B surface antigen and Hepatitis C antibody
- 12 lead EKG
- Patients will undergo pulmonary function tests as indicated in section 2.1.2
- Cardiac evaluation with possible stress test for patients with history of cardiac disease will be performed as indicated in section 2.1.2
- ECHO if prior history of doxorubicin
- Thoracic oncology consult for patients with pulmonary metastases
- Confirmation of pathology by the NCI Laboratory of Pathology [may be completed any time prior to enrollment]
- Radionuclide bone scan, when clinically indicated
- MRI Brain when indicated
- PET-CT when indicated

2.2.2 Within 4 weeks prior to treatment

- Baseline imaging: CT scan of chest, abdomen and pelvis (CT C/A/P) with triphasic 1mm cuts as per the liver scan protocol. For patients with evidence of hepatic disease, a baseline MRI-L will be performed.
- Completion of Health Related Quality of Life Forms (HRQOL)

2.2.3 Within 2 weeks prior to treatment

- Complete history and physical examination including vital signs, height and weight as well as ECOG assessment.
- Laboratory evaluation
 - CBC with platelets
 - Chem-20 (Sodium (Na), Potassium (K), Chloride (Cl), total CO₂ (bicarbonate), Creatinine, Glucose, Urea nitrogen (BUN), Albumin, Calcium total, Magnesium total (Mg), Inorganic Phosphorus, Alkaline Phosphatase, ALT/GPT, AST/GOT, Total Bilirubin, Direct Bilirubin, LD, Total Protein, total CK,
 - C-reactive protein, Hg A1c, Ferritin, Prealbumin,
 - PT/PTT & INR,
 - Urinalysis
- Tumor markers as indicated (serum cortisol, 24 hour urine for cortisol, ACTH, DHEA, and LDH)
- Anesthesia consult

2.2.4 Within 1 week of surgical treatment:

- Beta HCG for women of child bearing potential

2.3 REGISTRATION PROCEDURES

Authorized staff must register an eligible candidate with NCI Central Registration Office (CRO) within 10 days of signing consent. A registration Eligibility Checklist from the web site (<http://home.ccr.cancer.gov/intra/eligibility/welcome.htm>) must be completed and sent via encrypted email to: NCI Central Registration Office [contact]. After confirmation of eligibility at Central Registration Office, CRO staff will call pharmacy to advise them of the acceptance of the patient on the protocol prior to the release of any investigational agents. Verification of Registration will be forwarded electronically via e-mail to the research team. A recorder is available during non-working hours.

2.4 STRATIFICATION PROCEDURES

Patients will be stratified in to 2 groups: those with peritoneal recurrence only and those with visceral metastatic disease.

3.2 PREOPERATIVE PATIENT MANAGEMENT

Patients will receive standard preoperative care as appropriate to the planned surgical intervention and the patient's underlying health status which may include:

- The day prior to surgery: Sequential Compression Devices (SCDS), incentive spirometry and appropriate bowel preparation regimen, and hydration
- The night before operation: Hibiclens® shower
- Beginning the night prior to the operation, the patients will be hydrated intravenously in preparation for the HIPEC with cisplatin.

Note: For patients undergoing hepatic resection, no anticoagulation will be given prior to operation. For patients receiving an epidural catheter heparin will not be given until the catheter has been successfully placed.

3.3 PATIENT MANAGEMENT IN THE OPERATING ROOM

- Patients will receive perioperative antibiotics and the first dose will be administered prior to incision.
- Epidural catheters should be considered in all patients. Decisions will be made by the anesthesiologist and the operating surgeon in full collaboration.
- SCDs will be “on” before induction of anesthesia.
- A central venous line, arterial line, and large bore catheters will be placed if blood loss is anticipated to be >500cc or at the discretion of the anesthesiologist in consultation with the surgeon.

3.4 PERITONEAL METASTASECTOMY AND CYTOREDUCTIVE SURGERY

- If there is evidence that the extent of disease is beyond the ability to be cytoreduced such that the largest residual tumor nodule is ≥ 1.0 cm, patients will not be considered for intraperitoneal cisplatin.
- For patients with primary peritoneal metastases without massive ascites or intestinal obstruction, all visible disease will be resected if technically feasible.
- Peritonectomy for patients with peritoneal disease includes the following: the right and left sub-diaphragmatic peritoneum, the falciform ligament, lesser and greater omentum, anterior, right and left abdominal wall down to the paracolic gutters and the pelvic peritoneum.
- Partial (limited) peritonectomy for patients with intra-abdominal disease without peritoneal disease includes (i.e., liver metastases without peritoneal disease): peritoneal attachment of the hepatic left lateral segment and the spleen, 2 cm along the incision at the anterior abdominal wall and the falciform ligament
- Organs may be resected en bloc if invaded by tumor. For example, the spleen is often involved in recurrent tumors from a left sided primary. Organs that may be resected include but are not limited to colon, small bowel, pancreas, spleen, and liver.
- If a colonic anastomosis is required, a diverting ileostomy will be performed. This will be reversed after appropriate healing of the anastomosis.
- After the cytoreduction has occurred and the patient is either a CCR 0 or CCR 1 then cisplatin heated intraperitoneal infusion will be conducted for 90 minutes at goals of at least 40°C.

3.5 INTRAPERITONEAL CHEMOTHERAPY HIPEC

- Perfusion
 - Two large bore catheters will be inserted through the abdominal wall, one over the right lobe of the liver and one in the pelvis. The abdominal fascia will be closed, and the catheters connected to a perfusion circuit.
 - The perfusion flow rate will be maintained at approximately 1.0 L/min as tolerated and a perfusate volume will be maintained which moderately distends the abdominal cavity this volume will vary depending on the amount of ascites in any given patient.

- Stable perfusion parameters are obtained and the peritoneal cavity is warmed to a minimum of 40° C prior to starting the clock for perfusion time.
- The perfusion will be continued for 90 minutes.
- During the perfusion, constant physical manipulation of the abdomen (shaking) will be maintained for the entire time to assure even distribution of the perfusate.
- Peritoneal temperature will be measured continuously by three probes placed immediately beneath the peritoneal surface on either side of the abdomen and in the pelvis.
- The patient's core temperature will be measured with an esophageal probe (which correlates well with pulmonary artery temperatures) and maintained at less than 41°C using a cooling blanket and ice packs as needed.
- At the end of the perfusion, the abdomen will be re-opened and the perfusate irrigated from the abdominal cavity.

3.6 MEDICATIONS

- Cisplatin will be calculated on ideal body weight (IBW). Ideal body weight will be calculated based upon the following formula:

$$\text{IBW (male, in kg)} = [(\text{Height in inches} - 60) \times 2.3] + 50$$

$$\text{IBW (female, in kg)} = [(\text{Height in inches} - 60) \times 2.3] + 45.5$$

- Cisplatin 250mg/m² will be diluted in 1 liter of 0.9% sodium chloride for injection as described in Section 11.1.3
- Sodium thiosulfate.
 - In order to limit the systemic toxicity of cisplatin, sodium thiosulfate will be administered by continuous intravenous infusion starting immediately prior to the perfusion and continuing for a total of 12 hours.
 - A loading dose of 7.5 gm/M² of sodium thiosulfate will be diluted in 150 cc of 0.9% sodium chloride for injection. This loading dose will be infused over 20 minutes beginning with the addition of cisplatin to the peritoneal perfusion circuit.
 - Immediately following this bolus dose an additional 25.56 gm/M² of sodium thiosulfate will be diluted in 1000 cc of 0.9% sodium chloride for injection for a maintenance infusion of 2.13 gm/M² per hour for 12 hours. The maintenance infusion will be delivered over 12 hours by Infusion Pump.

3.7 POST-OPERATIVE CARE

3.7.1 Patient Monitoring

- The patients will be monitored in the Intensive Care Unit for no less than 12 hours after surgical resection. Routine ICU monitoring of vital signs will be performed according to the patient's clinical status. While in the ICU, an attempt to keep urine output greater than 100cc/hour will be made when physiologically feasible until the sodium thiosulfate is completed.
- Patients will be discharged from the ICU at the discretion of the treating surgeon and in accordance with the institution policies.
- Following discharge from the ICU, vital signs (blood pressure, temperature, pulse, respirations) will be taken per routine (every 2-6 hours and as clinically indicated).
- Patients will receive routine post-operative care; early ambulation will be encouraged.

- Laboratory evaluations will include:
 - CBC, platelets, acute care, mineral and hepatic panel daily x 4 days and then every third day or as clinically indicated until discharge.
 - Tumor markers for new baseline will be obtained on the day of discharge as indicated.
- Other evaluations
 - Imaging studies as clinically indicated.

3.8 RESEARCH EVALUATIONS

- Circulating endothelial Cells may be collected - 16ml in CPT blue/black tubes
 - Within 1 month prior to surgery
 - 6 weeks (+/- 2 weeks) post surgery
 - Every 6 months (+/- one month) post surgery
- Blood will be transported to:

[name] - Cell Signaling Lab
[name]
[contact]

3.9 DISCHARGE

- Total hospitalization may be approximately 7-14 days.
- Patients who are discharged within this time frame should be able to tolerate an oral diet. Patients who have a prolonged hospitalization but are able to tolerate a diet may be discharged with home rehab/physical therapy.

3.10 POST DISCHARGE

- CBC weekly following discharge or until toxicities have resolved (less than grade 3 or baseline) and patient has recovered from nadir. This may be done through the patient's referring physician with the results faxed to [name] or her designee.
- Patients will return to clinic approximately 4-8 weeks following surgery for their 1st post-operative visit and will be followed as clinically indicated until recovery. Upon recovery from the surgical procedure, the following end of treatment evaluations will be performed:
 - Imaging studies to establish new baseline
 - Tumor markers as indicated
 - CBC, acute care, mineral and hepatic panel, CRP, Albumin, pre-albumin, ferritin, Hgb A1c if elevated pre-op.
 - Physical examination to include ECOG, weight and vital signs
 - QOL survey

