3.13 CRITERIA FOR REMOVAL FROM PROTOCOL THERAPY AND OFF STUDY CRITERIA

Prior to documenting removal from protocol therapy, effort must be made to have all subjects complete a safety visit approximately 30 days following the last dose of study therapy.

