7 SAFETY REPORTING REQUIREMENTS/DATA AND SAFETY MONITORING PLAN

7.1 DEFINITIONS

7.1.1 Adverse Event

An adverse event is defined as any reaction, side effect, or untoward event that occurs during the course of the clinical trial associated with the use of a drug in humans, whether or not the event is considered related to the treatment or clinically significant. For this study, AEs will include events reported by the patient, as well as clinically significant abnormal findings on physical

examination or laboratory evaluation. A new illness, symptom, sign or clinically significant laboratory abnormality or worsening of a pre-existing condition or abnormality is considered an AE. All AEs must be recorded on the AE case report form unless otherwise noted above in Section 6.3.2.

All AEs, including clinically significant abnormal findings on laboratory evaluations, regardless of severity, will be followed until return to baseline or stabilization of event. Serious adverse events that occur more than 30 days after the last administration of investigational agent/intervention and have an attribution of at least possibly related to the agent/intervention should be recorded and reported as per section 7.2.

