10.1.5 Toxicities

Cisplatin produces renal tubular toxicities associated with renal insufficiency and electrolyte, (i.e. magnesium, potassium, calcium, phosphate, bicarbonate) wasting which may result in significant hypomagnesemia and hypokalemia. Neurotoxicity manifests as both sensory and motor peripheral neuropathies. Cisplatin is also toxic to the 8th cranial nerve producing ototoxicity which consists primarily of deficits in high frequency auditory acuity, but may include vestibular abnormalities. Systemic administration of cisplatin at doses similar to those planned in this study are associated with significant nausea and vomiting and bone marrow suppression, particularly leukopenia and thrombocytopenia. Transient moderate elevations of hepatic transaminases, (i.e. AST, ALT) and acute systemic allergic reactions including anaphylaxis may also occur. The prior Phase I study of CHPP with cisplatin has not identified any regional intraperitoneal toxicity from cisplatin. The dose limiting systemic toxicity was renal toxicity at doses of 350 mg/M². No other systemic toxicities were identified at that dose level.

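### After discharge only a CBC is scheduled until the end-of-treatment panel, so a patient without a known abnormality has no scheduled creatinine or electrolyte test for about 14 to 49 days

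*Combined protocol and SAP*

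**What the plan says.** All references are to the combined protocol and SAP.

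- **In hospital (3.7.1):** "CBC, platelets, acute care, mineral and hepatic panel daily x 4 days and then every third day or as clinically indicated until discharge". Section 3.9 gives the expected stay: "Total hospitalization may be approximately 7-14 days".
- **At home (3.10):** "CBC weekly following discharge or until toxicities have resolved (less than grade 3 or baseline) and patient has recovered from nadir". The referring physician may do this test. No other laboratory test is named for this period.
- **Next scheduled chemistry (3.10):** the first clinic visit is about 4-8 weeks after surgery. The acute care, mineral and hepatic panels belong to a list introduced by "Upon recovery from the surgical procedure, the following end of treatment evaluations will be performed". That wording sets no latest date.
- **30-day contact (3.13):** "effort must be made to have all subjects complete a safety visit approximately 30 days following the last dose of study therapy". No tests are listed for it.
- **Known abnormalities (7.1.1):** "All AEs, including clinically significant abnormal findings on laboratory evaluations, regardless of severity, will be followed until return to baseline or stabilization of event".
- **Named toxicities (10.1.5):** "Cisplatin produces renal tubular toxicities associated with renal insufficiency and electrolyte, (i.e. magnesium, potassium, calcium, phosphate, bicarbonate) wasting", and also "bone marrow suppression, particularly leukopenia and thrombocytopenia". The same section gives renal toxicity as dose-limiting at 350 mg/m2 and reports that no other systemic toxicity was identified at that level.
- **Outside results (6.2.1):** creatinine is on the list of values captured in C3D when obtained elsewhere. Potassium and magnesium are not named.

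**The concern.** Section 10.1.5 names both marrow suppression and renal toxicity. The plan follows the marrow at home with a scheduled test but not the kidney, although the kidney set the dose limit in the institution's phase I trial (1.2.3). A CBC cannot show creatinine, potassium or magnesium.

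Section 7.1.1 covers a patient who leaves hospital with a recognised creatinine rise or low magnesium. What remains is the patient whose abnormality first appears, or first becomes significant, after discharge. Until the end-of-treatment evaluation, that abnormality is found only if a clinician decides to test. The main stake is the safety of that patient. A lesser one is ascertainment for the secondary morbidity objective (1.1.2).

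**Working it through.** The plan states no figure for this interval, so there is none to reproduce. The check is interval arithmetic on the schedule.

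**Inputs**
- Discharge at day 7 or day 14 (3.9), assuming the stay is counted from the operation.
- First clinic visit at 4-8 weeks, that is day 28 or day 56 (3.10). The panels are assumed to be drawn at that visit, the earliest the section provides for.
- Safety visit at day 30 (3.13). The single perfusion is on the day of surgery, so days from last dose equal days from operation.
- The acute care and mineral panels are assumed to contain creatinine, potassium and magnesium; the protocol does not list their contents. If they do not, the gap is longer.

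**Gap from discharge to next scheduled chemistry** = evaluation day - discharge day

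| Discharge | Evaluation | Gap |
|---|---|---|
| day 14 | day 28 | 28 - 14 = 14 days |
| day 7 | day 28 | 28 - 7 = 21 days |
| day 14 | day 56 | 56 - 14 = 42 days |
| day 7 | day 56 | 56 - 7 = 49 days |

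The 49 days are not a ceiling, because the panel waits for recovery. The last inpatient draw may also precede discharge by up to about 3 days, so the interval between two chemistry results can be slightly longer.

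**Inpatient comparison.** If the every-third-day rule is followed, panels fall on days 1, 2, 3, 4 and 7 for a 7-day stay (5 panels), and also on days 10 and 13 for a 14-day stay (7 panels).

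**If chemistry were done at the 30-day visit.** The gap from discharge would be 30 - 14 = 16 to 30 - 7 = 23 days, followed by up to 56 - 30 = 26 days to a day-56 evaluation.

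**If panels were added to the weekly CBC.** The interval would be 7 days while draws continue. Extra tubes per patient over the gap: 14/7 = 2 to 49/7 = 7.

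**Dose context.** 350/250 = 1.4, so the dose-limiting level was 40% above this trial's dose.

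**The case against.** The strongest reply is that nothing in the documents shows late toxicity to be a problem here. Patients have already spent 7-14 days under repeated inpatient chemistry after a single perfusion. The dose is below the one that was limiting, and thiosulfate is given to limit systemic exposure (3.6). Section 1.2.4 describes earlier use of cisplatin with hyperthermia as safe. This stands to the extent that neither onset times nor rates are given, so the number of events that might be missed cannot be estimated. It weakens the electrolyte part most: electrolyte wasting is listed as a general cisplatin toxicity, but 10.1.5 reports no systemic toxicity other than renal at 350 mg/m2.

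Second, the upper end of the range may seldom occur. The 30-day visit overlaps the start of the 4-8 week window, the two may be one visit, and clinically indicated testing is always open. That is fair, but 3.13 requires only effort and names no tests, and 6.2.1 is a capture rule that orders nothing. None of these guarantees a result.

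Third, the trial record would gain little. Section 6.3.2 already keeps grade 1 and 2 events after discharge out of C3D, so mild changes would stay in source documents even if they were measured. This also stands.

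A reader might go further and infer that a related creatinine rise found after day 30 would be lost because 6.3.2 then takes only serious, unexpected and related events. The documents do not support that. Section 6.3.2 does not say whether onset or detection date governs. All adverse events are described in source documents (6.3). Related grade 3-4 events and all serious events are tabulated for the IRB (7.2.2), and serious events after day 30 that are at least possibly related are recorded and reported (7.1.1).

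**Conclusion.** The point holds as a minor one. For a patient without a known abnormality, no renal or electrolyte test is scheduled for about 14-49 days after discharge, and for longer if recovery is slow. The range rests on the protocol's approximate timings and on the assumptions listed in the working. A 30-day visit that happened to include chemistry would shorten the first gap to 16-23 days.

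The case rests mainly on creatinine, and the benefit is earlier detection for patient safety. Two stronger readings might be inferred and are not supported. One is that renal toxicity goes unfollowed after discharge: 7.1.1 requires known, clinically significant findings to be followed. The other is that the morbidity results will be materially understated: no rate or onset time allows that to be shown. The primary endpoint, intraperitoneal progression-free survival, is unaffected.

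**What to change.** 1. **Section 3.10:** keep the CBC and add the acute care and mineral panels to the same draw, stating that they include creatinine, potassium and magnesium. Apply the continue-until-resolved rule to those values as well, so that an abnormal result keeps the draws going after the blood count has recovered.
2. **Section 3.13:** list the same panels for the 30-day safety visit. This gives a planned result even where the weekly draws have stopped early, at about the time the narrower C3D rule in 6.3.2 begins.
3. **Section 6.2.1:** add potassium and magnesium to the outside-laboratory values captured; creatinine is already there.

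No change to treatment, eligibility or endpoint is needed.

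**Cost:** one more tube at each existing draw, typically 2-7 per treated patient. If 30 patients each had 7 draws, that is 30 x 7 = 210 tubes. This is a rough guide and not an upper bound: delayed recovery adds draws, while early stopping of the CBC, or patients who never receive cisplatin, reduce them. There is also the amendment wording and some extra collection and entry of outside results.
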